11. DATA MANAGEMENT

Data management, analysis and reporting of trial data collected from all randomised subjects will be prepared by the MRC CTU at UCL according to the Data Management Plan and Statistical Analysis Plan.

11.1 Data management at the Clinical Centre

Staff at the clinical centre will be responsible for:

- Creating medical notes for each participant which includes paper copies of the consent documents and the blood results
- Entering information relevant to eligibility and emergent adverse events and documenting the result of any pregnancy tests and urinalysis in the medical notes
- The accurate completion of the CRFs
- Collection and review of the diary cards from participants
- Notification of SAEs within 24 hours of becoming aware of the event to the MRC CTU Project Manager/Monitor and the JRCO
- Notification of pregnancy within 24 hours of becoming aware of the pregnancy to the Chief Investigator
- From 1st May 2017, notification of SUSARs within the timelines defined in Section 8 and maintaining the Trial Master File.

The dates of visits including immunisation dates, and details of clinical management (description of

significant adverse events and concomitant medication) will be documented in the medical notes. The CRFs will not bear the participant's name. The participant's initials, date of birth and trial number (which will have been given at screening) will be used for identification. A member of the clinical trial team must sign the laboratory and ECG reports. In the event of an abnormality, an indication should be given whether or not the abnormality is clinically significant, the date of review and the signature of the clinician reviewing the result. The database and medical notes should be kept in a secure location for 2 years after the last approval of a marketing application or until 2 years have elapsed since formal discontinuation of product development, and at least 15 years after the clinical trial has ended.

11.2 Data Management in the Immunology Laboratories

Standard operating procedures will be followed in all laboratories to ensure the quality of the data. Data will be stored electronically and transferred in an agreed format for analysis.

11.3 Data management at the MRC CTU at UCL

Staff at the MRC CTU will be responsible for:

- Designing the CRFs
- Creating a database
- Training staff at the clinical centre in data collection and overseeing data entry which may include data entry at the clinical centre directly into the database
- Notification of SUSARs within the timelines defined in **section 8**
- Drafting the Data Management and Statistical Analysis Plans and conducting the analyses
- Clinical site monitoring
- Maintaining the Trial Master File on behalf of the sponsor until 1st May 2017
- Coordination of the Trial Management Group

12. TRIAL MONITORING

12.1 Risk Assessment

The MRC will perform a risk assessment to assess the risks and benefits of trial participation to individual participant safety, as well as the risks that underlie the validity of the trial results with respect to safety and immunogenicity outcome measurements.

The risk assessment will be reviewed by the Chief Investigator.

This assessment will be used to guide the development of procedures with respect to informed consent, confidentiality, trial monitoring and audit.

12.2 Monitoring by Medical Research Council Clinical Trials Unit at University College London (MRC CTU at UCL)

Monitoring will be performed according to ICH-GCP. A monitoring plan will be written based on the risk assessment.

On-site monitoring will be delegated to a trained monitor by the MRC CTU at UCL to ensure that the study is conducted in compliance with the protocol, is consistent with SOPs, the principles of GCP, applicable regulatory requirements and locally accepted practices. The investigators, as well as volunteers through consenting to the study, agree that the monitor may inspect study facilities and source records (e.g., informed consent forms, clinic and laboratory records, other source documents), as well as observe the performance of study procedures. Such information will be treated as strictly confidential and will under no circumstances be made publicly available.

The Principal Investigator will permit inspection of the facilities and all study-related documentation by authorised representatives of the Sponsor, and Regulatory Authorities responsible for this study.

Prior to the first volunteer being screened, a site initiation visit will be made by the MRC CTU and will consist of review of protocol and trial documents, training with respect to trial procedures (informed consent, SAE reporting, inclusion and exclusion criteria), review of recruitment strategy, review of site facilities and equipment, essential document receipt, collection and filing, and archiving and inspection. Copies of the trial specific documents will be given to the investigators. The approved version of the protocol should be followed at all times, and any significant protocol deviations will be documented on a Protocol Deviation Form and submitted by MRC CTU to the Sponsor as soon as possible. The investigators will allow the monitors to:

- Inspect the site, the facilities, IMP management and materials used for the trial
- Meet all members of the team involved in the trial, and ensure all staff working on the trial are experienced and appropriately trained, and have access to review all of the documents relevant to the trial
- Have access to the case report forms and source data
- Discuss with the investigator and site staff trial progress and any issues on a regular basis

12.3 Monitoring by the Imperial CRF

From 01 May 2017, MRC CTU at UCL will cease to perform monitoring and that responsibility will transfer to the Imperial CRF.

12.4 Clinical Site Monitoring

The trial site will be monitored to ensure that:

- All participant records exist; participants are eligible and informed consents signed
- There is adherence to the protocol, including consistency with inclusion/exclusion criteria

- There is compliance with the principles of GCP and regulatory requirements
- Trial Documentation is complete and up to date (e.g. correct versions of documents being used, source data captured) and relevant documents are collected for the Trial Master File (TMF)
- The CRFs have been completed correctly and accurately, and all entries correspond to data captured in source documents
- The IMP accountability records are in order (receipt, dispensing and return/destruction), storage is under appropriate conditions and secure, expiry dates are being checked and adhered to, and dispensing is according to the protocol and trial procedures.

All information dealt with during such visits will be treated as strictly confidential. At the end of the trial, a close out visit will be performed by the monitor after the final participant visit has been completed and prior to database lock. During this visit the monitor will verify that all trial close out activities are completed – all queries resolved, missing data completed, monitoring completed, archiving arrangements in place, IMP accountability complete and all used and unused IMP returned/destroyed, ISF (investigator site file) completed and TMF documents collected, and end of trial notified. Each investigator will also be notified that an audit or inspection may be carried out - by the sponsor; sponsor's representatives or the regulatory authorities - at any time, before, during or after the end of the trial. The investigator must allow the representatives of the audit or inspection team:

- To inspect the site, facilities and material used for the trial
- To meet all members of his/her team involved in the trial
- To have direct access to trial data and source documents, to consult all of the documents relevant to the trial

12.5 Monitoring by the Trial Management Group

The Trial Management Group (see **section 16.1**) will monitor the following:

- Screening and enrolment numbers
- Immunisations completed and any missed or outside the window
- Adverse events of note
- Missed visits and loss to follow-up
- Logistical difficulties at the clinical centre
- Data management issues (timeliness of CRFs, completeness)
- Immunology core lab issues (completeness of specimen collection, next batch transfer or analysis)
- GCP issues (minor or other breaches)

12.6 Confidentiality

The principles for the UK DPA will be followed. All personal details of the participants and the results of the trial will be kept strictly confidential. The Sponsor, as represented by the ICL JRCO, will not keep any material on file containing the volunteers' full names; this information will be kept by trial team in the clinical trial facilities in a secure location. The confidentiality of volunteers will be respected and maintained at all times.

Each participant's GP will be notified of their patient's participation in the trial.

13. ETHICAL CONSIDERATIONS AND APPROVAL

13.1 Ethical Issues

There are three aspects of this trial that raise ethical issues

First, safety: DNA plasmid vaccines have been widely used in man at similar doses to those employed in this trial to vaccinate against a wide range of infectious diseases such as HIV as well as non infectious diseases such as cancer. To date, there have been no safety concerns. Also such vaccines have been administered via conventional methods such as IM and ID as well as using EP.

Second, issues particular to HIV: because the product under investigation is a **candidate HIV vaccine**, and HIV is transmitted sexually. The nature of the product may lead volunteers to erroneously conclude they are protected against HIV and to engage in riskier behaviour as a consequence. It is possible that following immunisations, participants may have equivocal results in the standard laboratory tests for HIV. However, any accredited laboratory would be able to distinguish between a response to the vaccine and the occurrence of a natural infection using routine assays.

Third, financial: **the reimbursement** to compensate for the intense follow-up schedule, which is a feature of healthy volunteer trials, could be sufficient incentive for individuals to take part against their better judgement. However, the rate of reimbursement in this trial is in line with those of similar healthy volunteer trials.

13.2 Ethical Considerations

The trial will be conducted in compliance with the approved protocol, UK Clinical Trial Regulations and any amendments, which include compliance with the principles of Good Clinical Practice (GCP) and will abide by the principles of the Declaration of Helsinki, the UK Data Protection Act (DPA number: Z5886415), and the National Health Service (NHS) Research Governance Framework for Health and Social Care (RGF).

The trial proposal including the trial specific information to be provided to volunteers will be reviewed by a recognised Research Ethics Committee (REC) and by the Medicines and Healthcare products Regulatory Authority (MHRA). The trial will not proceed unless the sponsor obtains approvals from these two authorities.

All volunteers must give written consent to participate in this trial, before any screening evaluation. Before giving consent, volunteers will be asked to read the information sheet about the trial and raise questions. They must also read the consent form. They will have the opportunity to discuss the trial with the Principal Investigator or delegate, and be asked to explain what the trial involves in their own words, to ensure the volunteer understands the intensity of the schedule and the issues associated with taking part in a trial of a candidate HIV vaccine.

The safety assessments are intense. Participants will be asked to remain in clinic for about 1 hour following each immunisation, to complete a diary card for at least 7 days thereafter, respond to a 'safety [telephone] call' the day after each immunisation, and return for a safety visit a week (-3 days/+ 7 days) after each immunisation. They will be advised to call the clinic staff if they are concerned, and 24 hour cover will be available.

14. INDEMNITY

The Sponsor for the trial is Imperial College London (ICL).

The Sponsor undertakes to compensate any volunteers for injuries which are considered, on the balance of probabilities to have arisen as a result of their participation in the trial regardless of whether the injuries were caused by negligence or not.

ICL holds insurance to cover participants for injury caused by their participation in the clinical trial. Participants may be able to claim compensation if they can prove that ICL has been negligent. However, as this clinical trial is being carried out in a hospital, the hospital continues to have a duty of care to the participant in the clinical trial. ICL does not accept liability for any breach in the hospital's duty of care, or any negligence on the part of the hospital employees. This applies whether the hospital is an NHS Trust or not. This does not affect the participant's right to seek compensation via the non-negligence route.

Participants may also be able to claim compensation for injury caused by participation in this clinical trial without the need to prove negligence on the part of ICL or another party. Participants who sustain injury and wish to make a claim for compensation should do so in writing in the first instance to the Principal Investigator, who will pass the claim to the Sponsor's Insurers, via the Joint Research Compliance Office.

15. FINANCE

The clinical trial activities, acquisition of product, data management and analysis are funded by the EC under the FP7 framework.

Participants will receive recompense for their time and travel, £200 per vaccination visit and £100 per screening/safety/follow-up visit up to a total of £1600 over the course of the study. Only enrolled participants will be paid for the screening visit.

There are no bonuses or per participant incentives paid to staff.

16. TRIAL COMMITTEES

16.1 Trial Management Group (TMG)

The Trial Management Group (TMG) will be formed of the Chief, Principal and other lead Investigators (clinical and non-clinical) from the clinical centre and immunology laboratory as well as members of MRC CTU.

The TMG will be responsible for the day-to-day running and management of the trial and will be accountable to the Sponsor.

The TMG will also be responsible for the composition of the expert panel to review any emergent SUSARs.

16.2 CUT'HIVAC Consortium Governing Board

This Governing Board has reviewed the design of the trial.

The Governing Board will be notified by the Project Lead of the progress of the trial, and provided with the final Clinical Study Report.

The CUT'HIVAC Consortium funding ended in December 2015. Subsequently the accountability has been to the Project Coordinator at INSERM, France.

16.3 Trial Management Team (TMT)

Weekly clinical TMT meetings are held at the Imperial CRF, Hammersmith Hospital.

17. PUBLICATIONS

The preparation of a manuscript for publication in a peer-reviewed professional journal or an abstract for presentation, oral or written, to a learned society or symposium will be discussed on the Trial Management Group calls. The Sponsor will be notified of this intention through the Chief Investigator and the TMG notes. Every effort will be made to allow the Sponsor and other relevant parties involved in the clinical trial and named in the clinical trial agreement prepared by the Sponsor, 30 days to comment before any results are submitted. This timeline will be strictly observed for peer-review journals, but may be more difficult to adhere to for conference presentations. Approval from the Chief Investigator, the clinical centre Principal Investigator and Project Lead must be obtained as a minimum before submission to a conference.

Authorship should reflect work done by the investigators and personnel of the sponsor, in accordance with generally recognised principles of scientific collaboration.

18. PROTOCOL AMENDMENTS

After the protocol has been approved by the main REC and the MHRA, no changes may be made without the written agreement of the Chief Investigator and the sponsor.

The MHRA and main REC do not need to approve any substantial change to the protocol that needs to be implemented urgently to avoid an immediate hazard to trial participants. The sponsor will ensure that the MHRA and main REC are informed of urgent amendments in accordance with UK clinical trials regulatory guidance.

The REC and/or MHRA must approve substantial amendments before they are implemented.

EP is an efficient DNA delivery method that has been shown to significantly increase DNA vaccine potency by up to several orders of magnitude compared to delivery by conventional injection. EP is a technique for intracellular delivery based on the brief application of electrical fields in a target region of tissue. This process induces a transient state of membrane destabilization/permeability, during which time normally impermeant substances present in the interstitial space at the site of EP application can be taken up into the affected cells. Shortly after EP, the cell membrane stabilizes and the cells resume normal function. EP has been demonstrated to be a potent method for DNA delivery in a variety of tissues including skeletal muscle, liver, lung, skin, and various tumour types, enhancing intracellular DNA uptake and gene expression by 2-3 orders of magnitude compared to conventional methods of administration.

Properties of the TDS Technology

The TDS devices are designed for intramuscular or intradermal administration of DNA using EP. The TDS technology utilizes the *in vivo* application of electrical fields to enhance the intracellular delivery of agents of interest in a targeted region of tissue. Specifically, the device is designed applying electrical fields at the site of administration to induce the EP effect in the presence of the DNA to be delivered. The device has been designed for use in human clinical studies and complies with the applicable safety and electromagnetic compatibility requirements of the International Electrotechnical Commission (IEC) 60601-1.

TDS device components

Both the TDS-IM and TDS-ID consist of the following components:

- Pulse Stimulator
- Integrated Applicator
- Single use Application Cartridge

In addition, the TDS-ID device has a

- Medi-Jector Vision needle free injection device

The configuration of the TDS device is designed for the administration of investigational agents in the context of early phase human clinical studies.

Device Components

Pulse Stimulator

The Pulse Stimulator is an electronic device that controls the administration sequence, generates the electrical signals necessary to enhance the intracellular delivery of the agent, and monitors the administration sequence for safety hazards.

The Pulse Stimulator performs a comprehensive self-diagnostic to ensure that the device and all internal safety systems are functioning properly before an administration procedure can be initiated. The device has been designed to comply with the applicable safety and electromagnetic compatibility requirements of IEC.

Integrated Applicator

The Integrated Applicator is a reusable hand-held device that contains mechanisms to automatically deploy the electrodes into the tissue and administer the biologic agent. The device is configured so that the entire procedure is applied in an automated fashion following the activation the procedure initiation button. This ensures that the prescribed administration parameters (e.g. site of agent injection relative to EP application, rate of agent injection, and time interval between agent injection and EP application) will be implemented for every recipient in a uniform fashion, thereby minimizing variability in the application of the procedure arising as result of operator skill or level of training. A user activated mechanical safety switch reduces the possibility of an inadvertent discharge of the device during set up.

TDS-IM

TDS-ID

[figure not shown]
Application Cartridge

Each Application Cartridge is packaged sterile for single use and is the only component of the system that contacts the recipient

TDS-IM

The TDS-IM Application Cartridge is used to house the agent to be delivered (in a standard syringe) and the electrodes used for EP application. It is comprised of a plastic, injection molded body that encloses the four electroporation electrodes.

The TDS electrode array consists of four electrodes arranged in two equilateral triangles to form a diamond configuration around a central injection needle. With the long axis of the diamond placed in parallel with the direction of the muscle fibres this configuration corresponds with the ellipsoid fluid distribution characteristic of an intramuscular injection.

TDS-ID

The TDS-ID Application Cartridge consists of a plastic body that encloses the four electrode TriGrid™ array and interfaces with a Medi-Jector Vision needle free injection device containing the agent to be administered. It is attached to the Medi-Jector Vision syringe once it has been loaded with the dose to be administered.

Prior to administration, the electrodes remain recessed within the sterile Application Cartridge body. A plastic safety cap located on the tip of the cartridge protects the operator from accidental stick injury and ensures that the electrodes remain sterile prior to administration. Each Application Cartridge also incorporates a spring loaded stick shield that deploys over the electrodes as the device is retracted from the recipients skin. This facilitates safe and simple disposal of the single use Application Cartridge and ensures that the electrodes are never visible to the recipient

TDS-ID Medi-Jector Vision needle free injection device

The Medi-Jector Vision injection device and needle free syringe is filled to the prescribed dosage and inserted into rear aperture of the application cartridge. Once the syringe is inserted, tabs located on the cartridge body lock it into place to facilitate safe disposal.

APPENDIX 2: TOXICITY TABLE

Based on systems in use at the MRC CTU, IAVI and NIH Division of AIDS

Abbreviations:	ULN	Upper Limit of Normal	LLN	Lower Limit of Normal
	R _x	Therapy	Req	Required
	Mod	Moderate	IV	Intravenous
	ADL	Activities of Daily Living	Dec	Decreased

For other events not specified in the tables below the severity will be determined according to the US department of health and human services: *Guidance for Industry – Toxicity grading scale for Healthy adult and adolescent volunteers enrolled in Preventative Vaccine Clinical trials.*

<http://www.fda.gov/downloads/BiologicsBloodVaccines/GuidanceComplianceRegulatoryInformation/Guidances/Vaccines/ucm091977.pdf>

LABORATORY PARAMETERS

PARAMETER	GRADE 1 MILD	GRADE 2 MODERATE	GRADE 3 SEVERE	GRADE 4 EXTREME
HAEMATOLOGY				
Hb	10.0-10.9 g/dL	9.0-9.9 g/dL	7.0-8.9 g/dL	<7.0 g/dL
White Blood Count	13.0 – 14.9 x10 ⁹ /l or 2 – 2.5 x10 ⁹ /l	15.0 – 19.9 x10 ⁹ /l or 1.5 – <2.0 x10 ⁹ /l	20.0 – 29.9 x10 ⁹ /l or 1 – <1.5 x10 ⁹ /l	≥30.0 or <1.0 x10 ⁹ /l
Absolute Neutrophils	1.3-1.0 x10 ⁹ /l	<1.0-≥0.75 x10 ⁹ /l	<0.75-≥0.5 x10 ⁹ /l	<0.5 x10 ⁹ /l
Percent neutrophils	>80%	90%	≥95%	---
Lymphocytes	0.7- 0.899 x10 ⁹ /l	0.5-0.699 x10 ⁹ /l	0.35-0.499 x10 ⁹ /l	<0.35 x10 ⁹ /l
Platelets	100 –124.999 x 10 ⁹ /l	50 – 99.999 x 10 ⁹ /l	25 – 49.999 x10 ⁹ /l	<25.0 x10 ⁹ /l
CD4 Count	300-400/mm ³	<300mm ³	<200/mm ³	<100/mm ³
BIOCHEMISTRY				
Potassium				
Hyperkalemia	5.6 – 6.0 meq/L	6.1-6.5 meq/L	6.6-7.0 meq/L	>7.0 meq/L
Hypokalemia	3.0 – 3.4 meq/L	2.5 – 2.9 meq/L	2.0- 2.4 meq/L	<2.0 meq/L
Bilirubin				
Hyperbilirubinemia	>1.25 – 2.0 x ULN	>2.0 – 2.5 x ULN	>2.5 – 5 x ULN	>5 x ULN
Glucose				
Hypoglycaemia	2.3-2.4 mmol/l	2.1-2.2 mmol/l	1.5-2.0 mmol/l	<1.5 mmol/l
Hyperglycaemia nonfasting; no prior diabetes	7.0-10.0 mmol/l	10.1-15.0 mmol/l	15.1-25.0 mmol/l	>25.0 mmol/l
Transaminases				
AST (SGOT)	1.25 – 2.5 x ULN	>2.5 – 5.0 x ULN	>5.0 – 10.0 x ULN	> 10.0 x ULN
ALT (SGPT)	1.25 – 2.5 x ULN	>2.5 – 5.0 x ULN	>5.0 – 10.0 x ULN	> 10.0 x ULN
GGT	1.25 – 2.5 x ULN	>2.5 – 5.0 x ULN	>5.0 – 10.0 x ULN	> 10.0 x ULN
Alk Phos	1.25 – 2.5 x ULN	>2.5 – 5.0 x ULN	>5.0 – 10.0 x ULN	> 10.0 x ULN
Amylase	>1.0 – 1.5 x ULN	>1.5 – 2.0 x ULN	>2.0 – 5.0 x ULN	>5.0 x ULN
Creatinine	130-180 μ mol/l	181-360 μ mol/l	361-720 μ mol/l	>720 μ mol/l
URINALYSIS				
Proteinuria: 24 hour urine	200 mg - 1 g loss/day OR <0.3% OR <3 g/l	1 – 2 g loss/day OR 0.3 – 1.0% OR 3 - 10 g/l	2 – 3.5 g loss/day OR >1.0% OR > 10 g/l	Nephrotic syndrome OR >3.5 g loss/day
Haematuria	Microscopic only ≤10 RBC/HPF	>10 RBC/HPF	Gross, with or without clots OR RBC casts	Obstructive OR transfusion req

SOLICITED VACCINE REACTIONS

GENERAL				
Fever Oral>12 hours	37.7 - 38.9°C (100.0 – 101.5°F)	39.0 – 39.7°C (101.6 – 102.9°F)	39.8 – 40.5°C (103 – 105°F)	>40.5°C (105°F) OR max temp of >105°F
Chills/rigors	Mild hot/cold flush requires blanket or occasional over the counter treatment	Limiting daily activity >6 hours, or need regular over the counter treatment	Uncontrollable shaking, prescription treatment needed	Hospitalisation
Malaise/abnormal tiredness	Normal activity reduced – not bad enough to go to bed	Fatigue such that ½ day in bed for 1 or 2 days	Fatigue such that in bed all day or ½ day for more than 2 days	Hospitalisation
General (all over) muscle aches and pains	No limitation of activity	Muscle tenderness, aches/pains limiting activity e.g. difficulty climbing stairs	Severe limitation e.g. can't climb stairs	Hospitalisation
Headache	No treatment or responds to over the counter treatment	Regular over the counter or occasional prescription treatment needed	Regular prescription treatment needed	Hospitalisation
Nausea	Intake maintained	Intake reduced less than 3 days	Minimal intake 3 days or more	Hospitalisation
Nausea/vomiting	Less than 4 x a day or lasting less than 1 week	At least 4 x day or lasting 1 week or more	Unable to keep any food or fluids down	Hospitalisation
CUTANEOUS				
Discomfort/pain in injected muscle (including ache) or overlying skin	Mild itch or ache that responds to over the counter treatment, if needed	Pain requiring regular over the counter treatment or occasional prescription treatment	Pain requiring regular prescription treatment	Hospitalisation
Immediate reactions (within 6 hours of injection)	Symptoms of irritation locally (usually itching at the injection site) OR Erythema +/- swelling at the injection site		Laryngeal oedema insufficient to require intubation; diarrhoea insufficient to require IV fluids, or asthma insufficient to require hospitalisation OR Urticaria, angio-oedema OR Generalised pruritus	Anaphylactic shock
Erythema at injection site	Erythema up to and including 50% of baseline arm circumference OR Symptoms of irritation that are easily tolerated and do not require repeated medication OR Both	Erythema greater than 50% of the arm circumference at baseline With or without Symptoms of irritation that do not require repeated medication OR Symptoms of irritation that require repeated medication AND erythema up to and including 50%	Erythema greater than 50% of the arm circumference at baseline AND symptoms of irritation requiring repeated medication	Hospitalisation
Blistering or ulceration at injection site	Fluid filled vesicles or superficial disruption of epithelium covering an area < 1cm	Fluid filled vesicles or superficial disruption of epithelium, area 1 - 2cm OR Blood filled vesicles OR Full thickness disruption of epithelium healed within 2 weeks	Full thickness disruption of epithelium not healed within 2 weeks	Necrosis
Soft swelling – local	Swelling <25% of arm	Swelling 25-50% of arm	Swelling >50% of arm Or Induration/hardened swelling (when considered by the	

			clinician to be associated with a process arising in the muscle)	
--	--	--	--	--

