7.4.3.2 Urine

- protein, ketones, blood, leukocyte esterase, and nitrites – by dipstick

A urine specimen will be sent to the laboratory if the level of protein, blood, leukocyte esterase or nitrites is considered clinically relevant.

Various local and systemic adverse events are known to be associated with licensed vaccines, and are referred to as '**solicited adverse events**'. These include disturbances in routine laboratory parameters, and are described in **table 2** below.

Information on solicited adverse events will be collected on the day of each immunisation (pre-immunisation, and at 10 and 60 minutes post-immunisation), at a safety call the day after each immunisation and for the following 7 days through a structured interview and examination according to the schedule.

In addition systemic laboratory adverse events will be collected through routine laboratory testing according to the schedule. These will be recorded on the appropriate CRF page.

Participants will also be asked to complete a diary card recording solicited adverse events that start within 7 days of each immunisation.

Table 2: Solicited Adverse Events

Type	Event
Local AEs (immunisation site)	Discomfort Redness Swelling (soft) Induration (hard) Blisters
Systemic Clinical AEs	Abnormally raised temperature Chills Myalgia/flu-like general muscle aches Malaise (excess fatigue) Headache Nausea Vomiting
Systemic Laboratory AEs	Abnormalities in: Creatinine, AST, ALT, alkaline phosphatase, total bilirubin, glucose Hb, total WCC, neutrophils, lymphocytes, platelets

The events will be **graded** according to the study specific toxicity table (see **Appendix 2**).

Relationship to study product, which is defined in **section 8**, will be recorded in the immunisation CRF but not on the diary card, on the assumption that any of these events starting within 7 days of an immunisation are at least possibly related. If the onset is beyond 7 days, the event will be recorded on the adverse event CRF and a relationship determined by the investigator reviewing the event.

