10.2 Endpoints

10.2.1 Primary Endpoints

10.2.1.1 Safety

- Grade 3 or above local solicited adverse event (**Table 2**)
- Grade 3 or above systemic clinical and laboratory solicited adverse event (**Table 2**)
- Any grade of adverse event that results in a clinical decision to discontinue further immunisations
- Any grade of adverse event within 7 days of receiving intradermal and standard intramuscular vaccinations with or without electroporation

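### The Celsius and Fahrenheit fever limits in Protocol Appendix 2 disagree at the grade 1/2 and grade 2/3 boundaries, and no governing unit is named

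*Protocol*

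**What the plan says.** Protocol Appendix 2, under solicited vaccine reactions, has one row for fever, labelled "Fever Oral>12 hours". Its four grades read:

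- Grade 1: "37.7 - 38.9°C (100.0 – 101.5°F"
- Grade 2: "39.0 – 39.7°C (101.6 – 102.9°F"
- Grade 3: "39.8 – 40.5°C (103 – 105°F"
- Grade 4: ">40.5°C (105°F) OR max temp of >105°F"

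Protocol Table 2 lists "Abnormally raised temperature" among the solicited systemic clinical events, and the text beneath it in section 7.4 has these events graded "according to the study specific toxicity table". Protocol 10.2.1.1 and SAP 3.1.1 both name as a primary safety endpoint "Grade 3 or above systemic clinical and laboratory solicited adverse event". Protocol 7.4.2 specifies that temperature is taken orally but names no unit. No other section of either document says whether Celsius or Fahrenheit decides the grade.

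**The concern.** A bracketed second unit should restate the first. Here it gives different inner limits, so one temperature can receive two grades depending on which figure the grader reads.

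The grade 3 limit matters most, because several parts of the plan use it:

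- the grade 3+ solicited systemic component of the primary safety endpoint;
- SAP shell Table 2, which is restricted to grade 3+ solicited events and events leading to discontinuation;
- Protocol 2.2.4, which judges whether a route is explored further partly by the proportion of participants with a grade 3+ solicited event;
- footnote 8 to Protocol Table 5, under which a grade 3 report at the safety call brings an invitation back to clinic.

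The grade 1/2 limit matters less. It still reaches SAP Table 5b, which reports temperature by maximum grade.

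**Working it through.** **Inputs.** The printed limits of the fever row in Protocol Appendix 2, as quoted above.

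**Formulas.** F = C × 9/5 + 32, and C = (F − 32) × 5/9.

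**Step 1: convert each Celsius limit and compare it with the printed Fahrenheit figure.**

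| Limit | Celsius | Converted °F | Printed °F | Difference (°F) |
|---|---|---|---|---|
| Grade 1 start | 37.7 | 99.86 | 100.0 | 0.14 |
| Grade 1 end | 38.9 | 102.02 | 101.5 | 0.52 |
| Grade 2 start | 39.0 | 102.20 | 101.6 | 0.60 |
| Grade 2 end | 39.7 | 103.46 | 102.9 | 0.56 |
| Grade 3 start | 39.8 | 103.64 | 103 | 0.64 |
| Grade 3 end | 40.5 | 104.90 | 105 | 0.10 |

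The outer limits (37.7°C and 40.5°C) are reproduced to within rounding. The four inner limits are not: each is printed 0.5 to 0.6°F below its conversion.

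**Step 2: convert the printed Fahrenheit starts back.**

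- Grade 2: (101.6 − 32) × 5/9 = 38.67°C, against 39.0°C printed; gap 0.33°C.
- Grade 3: (103 − 32) × 5/9 = 39.44°C, against 39.8°C printed; gap 0.36°C.

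**Step 3: grade each 0.1°C reading on both scales, rounding the converted value to 0.1°F.**

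| Reading (°C) | °F | Celsius grade | Fahrenheit grade |
|---|---|---|---|
| 38.7 | 101.7 | 1 | 2 |
| 38.8 | 101.8 | 1 | 2 |
| 38.9 | 102.0 | 1 | 2 |
| 39.4 | 102.9 | 2 | 2 |
| 39.5 | 103.1 | 2 | 3 |
| 39.6 | 103.3 | 2 | 3 |
| 39.7 | 103.5 | 2 | 3 |

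Three readings conflict at each inner boundary. At the outer ends only the rounding edges differ: 37.7°C (99.9°F) falls just below the printed 100.0°F, and 105.0°F (40.56°C) just above the printed 40.5°C.

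**Step 4: size in the analysis.** With 8 participants per group, one participant moved across the grade 3 limit changes that group's grade 3+ proportion by 1/8 = 12.5 percentage points. In SAP Table 3, 0 of 8 has a 95% interval of 0 to 32%, and 1 of 8 has 2 to 47%.

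**The case against.** The best defence is that Celsius plainly governs. It is printed first in every cell, the trial has one UK site, and the protocol's other temperature criterion (exclusion criterion 8) is in Celsius only. Protocol 10.4.4 also makes the clinician's grade the reported one when the diary card differs. This makes a Celsius reading likely, but it is inference and not a stated rule. The grade 4 cell weakens it, because its second criterion stands in Fahrenheit alone, outside the brackets.

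The defence is stronger on consequences. Three wider readings are tempting, and the documents do not support them.

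- A reader might infer that the unit decides whether a fever is a primary safety event at all. It does not for a fever within 7 days of vaccination. Protocol 10.2.1.1 and SAP 3.1.1 also list adverse events of any grade in that period, so such a fever qualifies at grade 2 or grade 3. If SAP 4.5.1 is read as comparing participants with any endpoint in 3.1.1, the Fisher comparison does not move. Only the grade 3+ component and the tables built on it can.
- A reader might infer that a misgraded fever could readily stop dosing. The individual discontinuation rule (Protocol 6.1.5) and the hold rule (Protocol 7.5) also require the event to be confirmed, related and unresolved within 72 hours, and the hold needs 3 or more participants. Protocol 8.1 settles relatedness for solicited events starting within 7 days, by classing them as adverse reactions. The other conditions remain.
- A reader might start the grade 2/3 conflict at 39.4°C. That reading is 102.9°F, which is grade 2 on both scales.

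The row's duration qualifier narrows the practical reach further.

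**Conclusion.** The fever row is wrong as written. Its Fahrenheit limits are not conversions of its Celsius limits at the grade 1/2 and grade 2/3 boundaries, by about 0.6°F, which exceeds rounding. The effect is confined to 39.5–39.7°C (grade 2 or 3) and 38.7–38.9°C (grade 1 or 2).

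The conversions rest on nothing beyond the printed limits. The list of affected readings assumes recording to 0.1 degree. Any effect on results also requires a participant's qualifying fever to peak in one of these bands and graders to differ, or to be uncertain, about the unit. The documents give no expected fever rate, so the likelihood cannot be stated. This is a minor point, worth correcting because it concerns a threshold used in a primary safety component.

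**What to change.** Reconcile the Celsius and Fahrenheit limits in the fever row of Protocol Appendix 2, including the Fahrenheit-only criterion in the grade 4 cell. State the single unit used for grading on both the CRF and the diary card. Delete the other unit or convert it correctly. Which set of limits to keep is for the sponsor and investigators to decide.

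The cost is one corrected table row and a sentence naming the unit, carried through to the CRF and diary card wherever they reproduce the limits. No endpoint definition, sample size or analysis method changes. If temperatures have already been graded, those in the two conflicting bands should be checked against the unit adopted.
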